### **3.5.2. Laboratory Data**

Serum samples will be obtained for immunogenicity testing at Visit 1 (Month 0, immediately before Dose 1) and Visit 5 (Month 7, 1 month after Dose 3). Both toxin A- and toxin B-specific neutralizing antibody levels will be measured.

### **3.5.3. Reactogenicity Data**

The reactogenicity data collected in the study e-diary will include local reactions (erythema/redness, induration/swelling, and pain at injection site) and systemic events (fever, vomiting, headache, fatigue, new or worsening muscle pain, and new or worsening joint pain). The e-diary will record reactogenicity data from Day 1 to Day 7 starting on the day of each vaccination.

All reactogenicity endpoints will be summarized as proportions of subjects with events, by vaccine group. Additionally, exact 2-sided 95% CIs for proportions will be provided as applicable.

A descriptive summary will be presented for each vaccine lot, the pooled lots, and the control group. For Tier 1 and Tier 2 events, comparison between the pooled lots and the control group will be performed.

Point estimates and the exact 2-sided 95% CIs (using the Clopper-Pearson method) will be provided for proportions of subjects reporting each event.

The proportion of subjects reporting local reactions at the injection site (pain, erythema, and induration), and systemic events (fever, vomiting, headache, fatigue, new or worsening muscle pain, and new or worsening joint pain), on any day within the 7-day period after vaccination will be descriptively summarized by vaccine lot, by pooled lots and control group, and by each vaccination. Severities of local reactions and systemic events reported after each vaccination will also be descriptively summarized by vaccine lot, pooled lots, and control group. Exact 2-sided 95% CIs will be presented with the proportions.

### 3.5.3.1. Local Reaction Endpoints

#### Local Reactions: Presence or absence

The presence of redness or swelling is to be recorded in the e-diary as “yes” or “no.” If redness or swelling is present, then a second question is to appear requesting the size of the affected area; otherwise, no question is to appear. A measuring device with a scale ranging from 1 to 21 is to be used to measure the largest diameter in whole-number increments.

Measurements are to be rounded up to the nearest whole number. If the area is larger than the measuring device can measure, “21+” is to be selected. Measuring device units are converted to centimeters according to the following scale: 1 measuring device unit = 0.5 centimeters.

The presence of redness and swelling is defined according to the following scale:

= ., if missing

= “No,” if no or minimal redness or swelling is present, <2.5 cm (<5 measuring device units)

= “Yes,” if  $\geq 2.5$  cm ( $\geq 5$  measuring device units)

These categories (., “no,” “yes”) will be used for derivation of the variables below. For the data summary of the presence (“yes” or “no”) of a local reaction, the following variables are required:

CCI

- Presence of each local reaction on any day (Day 1 to Day 7) after each vaccination and after any vaccination.

CCI

- Presence of any local reaction on any day (Day 1 to Day 7) after each vaccination and after any vaccination.

The derivation of CCI “any day” variable is given in Table 4.

**Table 4. Derived Variables for Each Local Reaction**

Variable	Yes (1)	No (0)	Missing (.)
CCI			
Any day (Day 1 to Day 7)	Subject reports the reaction as “yes” on any day (Day 1 to Day 7)	Subject reports the reaction as “no” on all 7 days or as a combination of “no” and “missing” on all 7 days	Subject did not report on the reaction on any of the 7 days

For any local reaction on any day, a similar rule applies as specified in Table 5.

**Table 5. Derived Variables for Any Local Reaction**

Variable	Yes (1)	No (0)	Missing (.)
CCI			
Any day (Day 1 to Day 7)	Subject reports any reaction as “yes” on any day (Day 1 to Day 7)	Subject reports all reactions as “no” on all 7 days or as a combination of “no” and “missing” on all 7 days	Subject did not report on any of the reactions on any of the 7 days

### Maximum Severity for Local Reactions

Erythema/redness and induration/swelling are measured and recorded in measuring device units (range: 1-21+) and then categorized as absent, mild, moderate, or severe based on the grading scale in Table 6. Pain at the injection site will be assessed by the subjects as mild, moderate, or severe according to the grading scale in Table 6. Only an investigator or a medically qualified person is able to classify a subject’s local reaction as Grade 4. Grade 4 could also be determined if a reaction is reported as an SAE.

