6.1.6. Unscheduled Visit for a Grade 3 or Suspected Grade 4 Reaction

If a Grade 3 local reaction ([Section 7.1.1.2](#)), systemic event ([Section 7.1.1.3](#)), or fever ([Section 7.1.1.4](#)) is reported in the e-diary data, a telephone contact should occur to ascertain further details and determine whether a site visit is clinically indicated.

If a suspected Grade 4 local reaction ([Section 7.1.1.2](#)), systemic event ([Section 7.1.1.3](#)), or fever ([Section 7.1.1.4](#)) is reported, a telephone contact or site visit should occur to confirm whether the event meets the criteria for Grade 4. Only an investigator or medically qualified person is able to classify a subject's local reaction as Grade 4.

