7.1.1.4. Fever

In order to record information on fever, a digital thermometer will be given to subjects with instructions on how to measure oral temperature at home. Temperature will be collected in the e-diary in the evening daily during the e-diary reporting period. It will also be collected at any time during the e-diary data collection periods that fever is suspected. Fever is defined as an oral temperature of $\geq 38.0^{\circ}\text{C}$ (100.4°F). The highest temperature for each day will be recorded in the e-diary. Temperature will be measured and recorded to 1 decimal place and then categorized during analysis according to the scale shown in Table 3.

If a Grade 3 fever is reported in the e-diary, a telephone contact should occur to ascertain further details and determine whether a site visit is clinically indicated. Only an investigator or medically qualified person is able to classify a subject's fever as Grade 4. If a subject experiences a confirmed Grade 4 fever, the investigator must immediately notify the sponsor and, if it is determined to be related to the administration of the investigational product, further vaccinations will be discontinued in that subject. The Grade 4 reaction must be recorded in the CRF.

Table 3. Scale for Fever

Mild (Grade 1)	38.0-38.4°C (100.4-101.1°F)
Moderate (Grade 2)	38.5-38.9°C (101.2-102.0°F)
Severe (Grade 3)	39.0-40.0°C (102.1-104.0°F)
Potentially life threatening (Grade 4)	$>40.0^{\circ}\text{C} (>104.0^{\circ}\text{F})$

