8.3. Severity Assessment

GRADE	If required on the AE page of the CRF, the investigator will use the adjectives MILD, MODERATE, SEVERE, or LIFE-THREATENING to describe the maximum intensity of the AE. For purposes of consistency, these intensity grades are defined as follows:	
1	MILD	Does not interfere with subject's usual function.
2	MODERATE	Interferes to some extent with subject's usual function.
3	SEVERE	Interferes significantly with subject's usual function.
4	LIFE-THREATENING	Life-threatening consequences; urgent intervention indicated.

Note the distinction between the severity and the seriousness of an AE. A severe event is not necessarily an SAE. For example, a headache may be severe (interferes significantly with the subject's usual function) but would not be classified as serious unless it met one of the criteria for SAEs, listed above.

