**Table 6. Local Reactions Grading Scale**

	Mild (Grade 1)	Moderate (Grade 2)	Severe (Grade 3)	Potentially Life Threatening (Grade 4)
Pain	Does not interfere with activity	Interferes with activity	Prevents daily activity	Emergency room visit or hospitalization for severe pain
Erythema/ redness	2.5 cm to 5.0 cm (5 to 10 measuring device units)	>5.0 cm to 10.0 cm (11 to 20 measuring device units)	>10 cm ( $\geq 21$ measuring device units)	Necrosis or exfoliative dermatitis
Induration/ swelling	2.5 cm to 5.0 cm (5 to 10 measuring device units)	>5.0 cm to 10.0 cm (11 to 20 measuring device units)	>10 cm ( $\geq 21$ measuring device units)	Necrosis

The maximum severity (highest grading) of each local reaction within 7 days after each vaccination will be derived. The maximum severity will be derived as follows:

= ., if values are missing for all days (Day 1 to Day 7);

= 0, if the subject reports all reactions as “no” or a combination of “missing” and “no” for all days (Day 1 to Day 7);

= *highest grade* (maximum severity) within 7 days after vaccination, if the answer is “yes” for at least 1 day.

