#### **3.5.3.2. Systemic Event Endpoints**

Systemic events will be reported via e-diary. Subjects will be asked to assess severity of each event as mild, moderate, or severe as specified in [Table 7](#). Only an investigator is able to classify a subject’s systemic event as Grade 4, after physical examination or documentation from another medically qualified source.

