### 3.5.3.3. Temperature

Oral temperature will be collected in the e-diary, in the evening, daily for 7 days after vaccination. It will also be collected at any time during the e-diary data collection periods that fever is suspected. The highest temperature for each day will be recorded in the e-diary. The protocol defines fever as an oral temperature  $\geq 38.0^{\circ}\text{C}$  ( $\geq 100.4^{\circ}\text{F}$ ). Fever will be categorized as specified in Table 8.

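### The SAP lets an SAE report alone make a local reaction Grade 4, although Grade 4 redness and swelling are defined by tissue damage and not by seriousness

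*SAP*

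**What the plan says.** **Local reactions.** In SAP 3.5.3.1, under Maximum Severity for Local Reactions, one sentence begins "Only an investigator or a medically qualified person is able to classify a" and goes on to refer to a subject's local reaction as Grade 4. The next sentence adds: "Grade 4 could also be determined if a reaction is reported as an SAE". Table 6 follows. Its Grade 4 entry for pain is "Emergency room visit or hospitalization for severe pain". For redness it is necrosis or exfoliative dermatitis, and for swelling it is necrosis. Protocol 7.1.1.2 and its Table 1 give the same criteria and the same reservation to a qualified person, without an SAE route. They also say that a Grade 4 local reaction is recorded on the CRF and not in the e-diary.

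**Seriousness.** Protocol 8.3 says: "Note the distinction between the severity and the seriousness of an AE". Protocol 8.2.3 counts important medical events as SAEs even when they are not immediately life-threatening and need no admission.

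**Fever.** Protocol 7.1.1.4 says: "Only an investigator or medically qualified person is able to classify a subject's fever as Grade 4". It also has temperatures graded at the analysis stage from Table 3. SAP 3.5.3.3 says: "Fever will be categorized as specified in Table 8". Both tables put Grade 4 above 40.0°C. The SAP drops only readings below 35.0°C or above 42.0°C.

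**Systemic events.** SAP 3.5.3.2 says: "Only an investigator is able to classify a subject’s systemic event as Grade 4, after physical examination or documentation from another medically qualified source". Protocol 7.1.1.3 allows an investigator or another medically qualified person. For a suspected Grade 4, Protocol 6.1.6 says that "a telephone contact or site visit should occur to confirm whether the event meets the criteria for Grade 4".

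**The concern.** The word *also* makes the SAE report a second route to Grade 4, beside the qualified person's classification. A judgement that an event is serious is not a judgement that the tissue criterion in Table 6 was met. Because the sentence is permissive, it leaves open whether a given SAE changes the grade, and two programmers could produce different tables from the same data.

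Maximum severity is reported under the primary safety objective (SAP 6.1.2), and Grade 4 is its top category. Protocol 1.2.3.2 records that an earlier Phase 2 study was halted after seven cases of Grade 3 injection site redness. That was a lower grade and a formulation without aluminum hydroxide, so it says nothing about how often Grade 4 will occur here. It does explain why readers will look closely at the upper grades for redness.

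There is a side effect. Protocol 7.1.1.2 attaches consequences for further vaccination to a confirmed, related Grade 4 local reaction. A Grade 4 that exists only in the analysis table could make a subject handled according to the protocol look like a deviation.

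**Working it through.** **1. Does an SAE report imply the Table 6 criterion?**

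| Reaction | Grade 4 criterion (SAP Table 6, Protocol Table 1) | Does SAE status alone establish it? |
|---|---|---|
| Pain | Emergency room visit or admission for severe pain | Yes, if the SAE is an admission for severe pain; not if it is serious on other grounds |
| Redness | Necrosis or exfoliative dermatitis | No |
| Swelling | Necrosis | No |

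A hypothetical case: redness of 6 cm is 6 / 0.5 = 12 measuring device units, which is Grade 2 in Table 6 (11 to 20 units). If it is reported as an SAE without necrosis or exfoliative dermatitis, it stays Grade 2 by the table and may become Grade 4 by the added sentence.

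The mismatch also runs the other way. Protocol 8.2.4 says an emergency room visit is not necessarily a hospitalization, so pain that is Grade 4 through such a visit need not be an SAE. SAE status is neither sufficient nor necessary for Grade 4.

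**2. Fever.** Grade 4 is numeric in both tables, so grading a reading above 40.0°C as Grade 4 agrees with them. What is missing is the link to confirmation. Protocol 6.1.6 and 7.1.1.4 call for a suspected Grade 4 fever to be confirmed by a qualified person. SAP 3.5.3.3 does not say what happens to a reading above 40.0°C and up to 42.0°C that the site finds to be wrong. The same tension sits inside Protocol 7.1.1.4.

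**3. Systemic events.** The SAP's condition (investigator, after examination or outside documentation) is stricter than the protocol's (investigator or medically qualified person, telephone contact or visit). An event could be Grade 4 under the protocol and not under the SAP. That difference can only lower the analysed count.

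**4. Size of one misgraded subject.** The plan gives no figure for Grade 4 reactions. The one design figure needed is the group size:

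- 263 evaluable per lot / (1 − 0.20) = 328.75, rounded up to 329
- 4 × 329 = 1316, as stated in Protocol 9.1
- pooled lots: 3 × 329 = 987

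The interval is Clopper-Pearson, as in SAP 5.2.1. For r = 0 the upper limit is 1 − 0.025^(1/n). For r = 1 the lower limit is 1 − 0.975^(1/n), and the upper limit is the 0.975 quantile of Beta(2, n − 1).

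| Group | Grade 4 subjects | Percent | Exact 95% CI (%) |
|---|---|---|---|
| One lot, n = 329 | 0 | 0.000 | 0.000 to 1.115 |
| One lot, n = 329 | 1 | 0.304 | 0.008 to 1.682 |
| Pooled, n = 987 | 0 | 0.000 | 0.000 to 0.373 |
| Pooled, n = 987 | 1 | 0.101 | 0.003 to 0.563 |

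**5. Reach.** The primary test uses Month 7 antibody concentrations. No reactogenicity grade enters it, so the test, its power and the total of 1316 stay as they are.

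**The case against.** The best defence of the sentence is that it names a data source. Grade 4 local reactions are not collected in the e-diary, so the analysis must find them elsewhere, and SAE reports are an obvious place. The wording is permissive, it follows directly on the reservation to a qualified person, and SAEs are reported by the investigator. Much of this stands: the sentence is not subject self-grading, and deleting it would discard a useful way of finding true Grade 4 reactions. But as written it lets the report determine the grade, and it does not ask whether a Table 6 criterion was met.

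It is also fair to say that Protocol 8.3 concerns the intensity scale on the AE page, which is not the reactogenicity scale. It supports the principle only. The direct conflict is with Table 6 and Protocol 7.1.1.2.

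A reader might infer three stronger claims that the documents do not support.

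- *That grading fever from the diary value contradicts the grading tables.* Both tables are numeric, and the protocol itself calls for categorization at analysis. The SAP also counts fever among systemic events, so its Grade 4 rule for those events can be read to cover fever. The SAP is silent on refuted readings; it does not direct that they be counted.
- *That the SAP as a whole over-counts Grade 4.* The systemic rule works in the other direction. The conflict there is also thin in practice, because every Grade 4 entry in Table 7 involves an emergency room visit or admission, which would ordinarily leave medical documentation. Under-counting is possible too, since SAP 6.1.2 describes maximum severity as taken from the diary.
- *That the trial's main conclusion is at risk.* It is not, as the last step of the working shows.

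**Conclusion.** The point holds for local reactions. Under SAP 3.5.3.1, redness or swelling reported as an SAE may be analysed as Grade 4 without the tissue criterion that both documents require. For pain leading to admission there is no conflict.

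Two secondary points remain. Numeric fever grading and the confirmation rule are not reconciled, and the two documents state different conditions for a Grade 4 systemic event. The latter is an inconsistency, not an over-count.

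The effect is confined to descriptive safety tables. One misgraded subject would appear as 0.30% in a lot or 0.10% in the pooled lots. Those percentages assume that every randomized subject is in the denominator; if subjects without a given dose or without diary data drop out of it, the percentages rise slightly. How many subjects would be misgraded, if any, cannot be derived from the documents. This is a modest but real defect in a primary safety summary, and it is cheap to cure.

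**What to change.** **SAP 3.5.3.1.** Replace the SAE sentence with:

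> SAE reports will be used to identify possible Grade 4 local reactions. A reaction is analysed as Grade 4 only if the investigator or medically qualified person recorded that a Table 6 Grade 4 criterion was met. SAE status alone does not set the grade.

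**SAP 3.5.3.3.** Add that a diary temperature above 40.0°C, up to the 42.0°C exclusion limit, that is refuted at the Protocol 6.1.6 contact is not tabulated as Grade 4 and is listed separately. State as well how a reading that was neither confirmed nor refuted is shown.

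**SAP 3.5.3.2 and Protocol 6.1.6 and 7.1.1.3.** Reconcile who may classify a systemic event as Grade 4 and on what evidence, so that one event has one grade in both documents. This review does not say which rule should prevail.

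The first two changes concern classification for analysis and leave clinical management alone. The cost is a few sentences and one listing. The downside is that CRF and SAE confirmation must be merged with the diary data before maximum severity is derived.

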**Table 6. Local Reactions Grading Scale**

	Mild (Grade 1)	Moderate (Grade 2)	Severe (Grade 3)	Potentially Life Threatening (Grade 4)
Pain	Does not interfere with activity	Interferes with activity	Prevents daily activity	Emergency room visit or hospitalization for severe pain
Erythema/ redness	2.5 cm to 5.0 cm (5 to 10 measuring device units)	>5.0 cm to 10.0 cm (11 to 20 measuring device units)	>10 cm ( $\geq 21$ measuring device units)	Necrosis or exfoliative dermatitis
Induration/ swelling	2.5 cm to 5.0 cm (5 to 10 measuring device units)	>5.0 cm to 10.0 cm (11 to 20 measuring device units)	>10 cm ( $\geq 21$ measuring device units)	Necrosis

The maximum severity (highest grading) of each local reaction within 7 days after each vaccination will be derived. The maximum severity will be derived as follows:

= ., if values are missing for all days (Day 1 to Day 7);

= 0, if the subject reports all reactions as “no” or a combination of “missing” and “no” for all days (Day 1 to Day 7);

= *highest grade* (maximum severity) within 7 days after vaccination, if the answer is “yes” for at least 1 day.

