**Table 7. Systemic Event Grading Scale**

	Mild (Grade 1)	Moderate (Grade 2)	Severe (Grade 3)	Potentially Life Threatening (Grade 4)
Vomiting	1-2 times in 24 hours	>2 times in 24 hours	Requires IV hydration	Emergency room visit or hospitalization for hypotensive shock
Headache	No interference with activity	Some interference with activity	Significant; prevents daily activity	Emergency room visit or hospitalization for severe headache
Fatigue/ tiredness	No interference with activity	Some interference with activity	Significant; prevents daily activity	Emergency room visit or hospitalization for severe fatigue
New or worsening muscle pain	No interference with activity	Some interference with activity	Significant; prevents daily activity	Emergency room visit or hospitalization for severe new or worsening muscle pain
New or worsening joint pain	No interference with activity	Some interference with activity	Significant; prevents daily activity	Emergency room visit or hospitalization for severe new or worsening joint pain

Abbreviation: IV = intravenous.

For each systemic event, the following variables will be available, similar to local reactions:

1. Each systemic event on **CCI** any day (Day 1 to Day 7) after each vaccination and after any vaccination.
2. Any systemic event (including fever as described in Section 3.5.3.3) on **CCI** any day (Day 1 to Day 7) after each vaccination and after any vaccination.
3. Maximum severity of each systemic event on any day (Day 1 to Day 7) after each vaccination and after any vaccination.
4. Maximum duration of each systemic event after each vaccination.
5. Onset day of each systemic event after each vaccination.
6. Onset day of any systemic event after each vaccination.

The derivation of these variables is similar to the derivation of the variables for local reactions (Section 3.5.3.1).

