**Reporting results:**

- The number and percentage of subjects reporting: (1) a reaction; (2) maximum severity, on **CCI** [REDACTED] any day during Day 1 to Day 7, and the associated 95% CIs

**Endpoints:** (1) Systemic events (fever, vomiting, headache, fatigue, new or worsening muscle pain, and new or worsening joint pain); (2) maximum severity as self-reported in the e-diary for up to 7 days following vaccination at Visit 1, Visit 2, and Visit 4

- Analysis time points: occurring on **CCI** any day during Day 1 to Day 7 following vaccination at Visit 1, Visit 2, and Visit 4
- Analysis population: SAF population
- Analysis methodology: point estimates and Clopper-Pearson CIs
- Supporting objective: primary safety objective

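### The rule for maximum severity of each local reaction assigns Grade 0 only when all reactions are absent, so read literally it leaves some analysed subjects with no severity category

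*SAP*

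**What the plan says.** SAP 3.5.3.1, under Maximum Severity for Local Reactions, sets the unit: "The maximum severity (highest grading) of each local reaction within 7 days after each vaccination will be derived". Three branches follow Table 6:

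- missing, if values are missing on all seven days;
- 0, "if the subject reports all reactions as" *no*, or as a combination of missing and *no*, on all days;
- the highest grade, if the answer is *yes* on at least one day.

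The same section has two tables for presence or absence. Table 4, for each reaction, begins its entries with "Subject reports the reaction as". Table 5, for any reaction, begins its *No* entry with "Subject reports all reactions as".

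SAP 3.5.3.2 extends the approach to systemic events: "The derivation of these variables is similar to the derivation of the variables for local reactions". SAP 6.1.2, which sits under Primary Endpoints, reports "The number and percentage of subjects reporting: (1) a reaction; (2) maximum severity" with 95% CIs in the safety population. SAP 5.3.1.1 excludes a subject from a reactogenicity analysis only if that dose was not given or the data are missing on all days.

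**The concern.** The variable is defined per reaction, but its zero branch carries the any-reaction condition. A subject who has one reaction and never has another then falls between the branches for the other. Maximum severity is tabulated as a primary safety output, so a literal program would produce a table with analysed subjects who appear in no row. A derivation in a SAP should be codable without having to infer what was meant.

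**Working it through.** The documents state no figure that depends on this rule, so there is nothing to reproduce. The check is logical, followed by an illustration of size.

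**One subject.** Take a complete diary with pain *yes* on one day and redness *no* on all seven days. For redness:

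- Missing branch: fails. The redness answers are present.
- Zero branch: fails. Not all reactions are *no*, because pain was *yes*.
- Graded branch: fails. Redness was never *yes*. Reading this branch across reactions does not help, because there is no redness grade to take.

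**All patterns.** Three reactions, each *yes* or *no*, give 2 × 2 × 2 = 8 patterns. The all-*no* pattern gives 0 for every reaction, and the all-*yes* pattern gives a grade for every reaction. In each of the other 6 patterns, every reaction that is *no* gets no value. If the zero branch refers to the single reaction, as Table 4 does, all 8 patterns give a value for every reaction.

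**Effect on the table.** Write p for the share with a given reaction, n for the share with no reaction at all, and q = 1 − p − n for the share with some other reaction but not this one.

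- Grades 1 to 4 contain the same subjects under either reading.
- Grade 0 should be 1 − p. Read literally it is n, so it is short by q.
- With all analysed subjects in the denominator (SAP 5.3.1.1), Grades 1 to 4 still total p, and all rows together total 1 − q.
- Only if the unassigned subjects are dropped does p become p/(p + n).

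**Illustration.** The rates are assumptions, since the documents give none: redness 5%, swelling 5%, pain 10% to 70%, independent of each other. Then n = (1 − pain) × 0.95 × 0.95.

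| Pain | n (literal Grade 0 for redness) | Correct Grade 0 | Shortfall q | Redness if unassigned subjects kept | Redness if dropped |
|---|---|---|---|---|---|
| 10% | 81.2% | 95% | 13.8% | 5% | 5.8% |
| 30% | 63.2% | 95% | 31.8% | 5% | 7.3% |
| 50% | 45.1% | 95% | 49.9% | 5% | 10.0% |
| 70% | 27.1% | 95% | 67.9% | 5% | 15.6% |

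For example, at pain 30%: n = 0.70 × 0.9025 = 0.632, q = 1 − 0.05 − 0.632 = 0.318, and 0.05/(0.05 + 0.632) = 0.073. With redness and swelling set equal at 2% to 10%, and pain at 10% to 70%, the dropped-subject column runs from 2.3% to 29.2%. The most common reaction is little affected: pain of 50% becomes 52.6% when redness and swelling are 5%.

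**The case against.** The strongest reply is that this is a wording slip whose meaning is settled elsewhere. The lead sentence says each local reaction. The same subsection lists absent as a category for redness and swelling. Protocol 7.1.1.2 and 7.1.1.3 list absent for pain and for systemic events. Table 4 assigns *No* per reaction, and the list of derived variables closing 3.5.3.1 again names maximum severity of each local reaction. On that footing, the zero branch can be taken to mean all daily reports of the one reaction, and the three branches are then exhaustive.

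The point about intent stands, and a careful programmer would probably code it correctly. The proposed reading of the words is strained, however, because Table 5 uses the same words for the any-reaction variable.

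A reader might go further and infer that severity percentages will be inflated, and more so in the vaccine arm than with saline. The documents do not support that. The missing code is reserved for subjects with values missing on all days, and SAP 5.3.1.1 keeps everyone else who received the dose in the analysis. Inflation would need a coding step that contradicts both. Nor do the documents give reaction rates from which to size a difference between arms.

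A reader might also infer that the gap reaches every diary item. SAP 3.5.3.2 and 3.5.3.3 say only that their derivations are similar. Fever is a single item graded from measured temperature, so an all-reactions condition has no natural place there.

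**Conclusion.** The rule is wrong as written, and the consequence is small. Read literally, it leaves analysed subjects with no severity category, makes the Grade 0 row too low by the share who had another reaction but not this one, and gives rows that do not add up to the analysed total. Grade 1 to 4 counts are unaffected, as is the presence/absence summary, which has its own rule in Table 4. Grade 1 to 4 percentages are also unaffected with the SAP 5.3.1.1 denominator. The SAP 6.1.2 output is descriptive, and the lot-consistency decision rule does not use it.

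The shortfalls in the illustration rest on assumed, independent reaction rates. The inflated percentages also require unassigned values to be dropped contrary to the SAP. They show what a coding error could do and do not predict a result.

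**What to change.** In SAP 3.5.3.1, make the Grade 0 branch refer to the single reaction, as Table 4 does: 0 if the subject reports *the reaction* as *no*, or as a mix of missing and *no*, on all days from Day 1 to Day 7. Keep the all-reactions condition for the any-reaction variables in Table 5. In 3.5.3.2, confirm that the similar derivation is applied event by event. Fever needs no separate change. The cost is one phrase and one confirming sentence, with no change to data collection, design or sample size.
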